6.3 Key Definitions

The following definitions will be used:

- Date of the First Study Treatment Administration: The date of the first study treatment administration is defined as the earliest date on which a study treatment was administered.
- Baseline: The Baseline value is defined as the last available valid, non-missing observation for each subject prior to first study treatment administration on Day 1. If day 1 assessment has time missing, it will be considered as the baseline.
- Change from Baseline: The change from Baseline value at each visit will be calculated for all continuous parameters using the following formula when both values are available:

$$\text{Change from Baseline Value} = \text{Result at specified visit} - \text{Baseline Value}$$

- % Change from Baseline: The % change from baseline value is defined as Change from Baseline divided by Baseline value. Study Day: The study day of an event is defined as the relative day of the event starting with the date of the first study treatment administration (reference date) as Day 1 (there will be no Day 0).

The study day of events occurring before the first study treatment administration will be calculated as:

$$\text{Study Day} = (\text{Date of Event} - \text{Date of First Study Treatment Administration})$$

For events occurring on or after Day 1, study day will be calculated as:

$$\text{Study Day} = (\text{Date of Event} - \text{Date of First Study Treatment Administration}) + 1$$

Study days will only be calculated for events with complete dates and will be undefined for events that are ‘Ongoing’ at the end of the study.

6.4 Multiple Comparisons and Multiplicity

No multiplicity adjustment will be carried out for this study.

Adverse Events:

For adverse events with unknown intensity (severity) or unknown relationship to study treatment, these will be imputed as follows:

- If the intensity (severity) of an adverse event is unknown/missing, the intensity will be imputed for the summary of adverse events as being the highest intensity, i.e., “Severe”.
- If the relationship to investigational product of an adverse event is unknown/missing, the relationship will be imputed for the summary of adverse events as being “Related”.

For adverse events, where either the onset time or end time (resolution time) is unknown, AE duration (in days) will be imputed as follows:

- If onset date is unknown

- and it cannot be confirmed that onset was prior to the start of dose administration, then the AE will be classified as treatment-emergent adverse events (TEAE), and AE duration will be shown on the listing as UNKNOWN.
- If onset time is unknown:
 - If the date of onset is known to be same as the date of first dose administration, and it cannot be confirmed that onset was prior to the start of dose administration the AE will be reported as TEAE.

6.6 Visit Display Conventions

Visit Label for Summary Tables:

The following visit labels will be used in table summary outputs as applicable. Visit window defined in section 6.7 will be applied. :

- Screening
- Baseline
- Day 1 Post-dose
- Week 1
- Week 2
- Week 3
- Week 4
- Week 5
- Week 6
- Week 7
- Week 8
- Week 9
- Week 10
- Week 11
- Week 12
- Week 13
- Week 14
- Week 15
- Week 16
- Week 17
- Week 18
- Week 19
- Week 20
- Week 21
- Week 22

- Week 23
- Week 24
- EOT¹
- Week 28
- EOS²

Visit Label for Data Listings:

For listings, CRF labels will be used.

[REDACTED]

[REDACTED]

[REDACTED]

[figure not shown]
[REDACTED]

[REDACTED]

[REDACTED]

[REDACTED]

[REDACTED]

7.1 All Screened Population (ASP)

Consists of all subjects who provided informed consent for the study.

7.2 Safety Population (SP)

Consists of all subjects who receive at least one dose of study drug. This analysis population is used for safety and efficacy analysis.

7.3 PK Analysis Population (PKAP)

Subjects in the safety population who have at least one measurable post-EQ101 exposure concentration.

[REDACTED]

[REDACTED]

[REDACTED]

8 SUBJECT SCREENING, ENROLMENT AND DISPOSITION

Subject enrolment information to be reported are listed below:

- Date of informed consent/reconsent
- Reconsent Version and Date
- Protocol Version
- Date of Eligibility Check at screening
- Subject ID

Subject disposition information to be reported are listed below:

- Subject ID
- Date received first study drug.
- Date of last Dose
- Study Completion Status
- Treatment Completion Status
- Date of Completion/ Discontinuation
- Reason for Discontinuation
- Date and reason for consent withdrawal

Counts and percentages for the number of Subjects Enrolled and Screen failed will be provided for the All Screened Population. Counts and percentages for the number of subjects dosed, Completed, withdrawn/Not Completed (with all reasons for not completion) treatment and study will be provided for the Safety Population.

Listings will be provided for the subject enrolment information (listed in above) and sorted by Subject ID for the All Screened Population. For the subject disposition information (listed in above), listings will be provided sorted by Subject ID for the Safety population, along with age, sex, race, and baseline weight (or Screening Weight for Screening Failures) of the Subject.

9 ANALYSIS POPULATION

The following analysis set information will be reported:

- Subjects included in Safety Population
- Subjects included in Pharmacokinetic Population

• [REDACTED]

Counts and percentages for these Subjects under different analysis sets will be provided using the Safety Population

Listings of analysis population will be provided sorted by Subject ID for the Safety Population, along with age, sex, race, and baseline weight of the Subject.

[REDACTED]

[REDACTED]

[REDACTED]

[REDACTED]

[REDACTED]

11 DEMOGRAPHICS AND BASELINE CHARACTERISTICS

11.1 Demographics

The demographics variables to be reported are listed below:

- Age (years)
- Sex
- Women of child-bearing potential
- Race
- Ethnicity
- Weight (kg) at Screening
- Height (cm) at Screening
- Body Mass Index (BMI) (kg/m²) at Screening

Above variables will be summarized using descriptive statistics (specified in section 6.2) for Safety Population. Demographics variables will also be listed under Safety Population, sorted by Subject ID along with age, sex, race and baseline weight of the Subject.

11.2 Pregnancy and Follicle Stimulating Hormone (FSH) Test

All available pregnancy (serum or urine) and FSH test results will be displayed in data listing and sorted by Subject ID for Safety Population, along with age, sex, race, and baseline weight of the Subject.

11.3 Serology

All available serology results (including human immunodeficiency virus (HIV), Hepatitis B surface antigen (HbsAg), Anti-hepatitis C virus (HCV) antibodies (if positive, HCV RNA measurement) will be displayed in data listing sorted by Subject ID for Safety Population, along with age, sex, race, and baseline weight of the Subject.

11.4 COVID-19 Test

All available COVID-19 polymerase chain reaction (PCR) or rapid antigen test (RAT) test results will be displayed in data listing sorted by Subject ID for Safety Population, along with age, sex, race, and baseline weight of the Subject.

12 MEDICAL HISTORY

Medical history listings will be provided, sorted by Subject ID for Safety Population, along with age, sex, race, and baseline weight of the Subject. Medical history is coded using MedDRA 25.1.

The summary of medical history and medical history for subjects with autoimmune or mental health conditions will be presented by SOC in the order of descending frequency and PT within SOC in the order of descending frequency of the total column. Preferred term will be ordered by the total % and if they are tied, they are ordered alphabetically. The count and percentages of subjects with autoimmune disease or mental health conditions at End of Treatment/Early Termination compared to Screening will be summarised by SOC and PT for stable, improved or worsened. A Subject will only be counted once under a SOC or PT term by the worst status among multiple occurrences (“Worsened” is worse than “Stable” and “Stable” is worse than “Improved”).

13 DISEASE HISTORY

Disease history listings will be provided, sorted by Subject ID for Safety Population, along with age, sex, race, and baseline weight of the Subject. The summary of disease history will be presented by visit and following assessments for Safety Population.

The disease history information collected are as follows.

- Screening
 - Between 35% and 50% scalp hair loss, as determined by the Severity Alopecia Tool (SALT)
 - Alopecia Totalis
 - Alopecia Universalis
- Week 0, Day 1
 - Current AA Episode
 - What is the current Scalp involvement of the current AA episode (please specify the type)?
 - Duration (<6 months, 6 months – 1 year, >1 year - 4 years and >4 – 7 years)
 - Does the current AA episode affect the scalp only?
- Body Parts Affected by AA
 - Eyelashes?
 - If yes, duration
 - Eyebrows?
 - If yes, duration
 - Body Hair (armpits, pubic hair, beard)?
 - If Yes, please specify the area(s)
 - If yes, duration
- Nail Changes
 - Is subject experiencing nail changes currently?
 - If yes:
 - Pitting
 - Koilonychia
 - Trachyonychia
 - Other
 - If Yes, please specify the Duration for the most prominent/severe nail change

In addition, baseline SALT score and baseline SALT score categories of <50, >=50 to <95, and >=95 will be summarized using descriptive statistics.

Count and percentage of Alopecia Areata History Status at End of Treatment for nail disease and body hair disease will also be presented by stable, improved and worsened.

14 PRIOR AND CONCOMITANT MEDICATION

All medications will be coded by Anatomical Therapeutic Chemical (ATC) using World Health Organization Drug Dictionary (WHO-DD) (the version of WHODRUG GLOBAL B3 September 2022). The version used for coding will be specified in the footnote of the relevant outputs.

Prior medications are defined as those started before the start date/time of first study drug administration. Concomitant medications are defined as the medications taken at least once after the start date/time of first study drug administration, up to the end of study visit. If a clear determination cannot be made as to whether the medication is concomitant or not due to missing or incomplete data, the medication will be treated as concomitant medication taken during the study. Alopecia Areata Treatment History at Day 1 is also collected.

The number and percentage of Subjects using at least one concomitant medication will be displayed together with the number and percentage of Subjects using at least one medication within each anatomical therapeutic class (ATC-Level 1) and preferred name. It will be repeated for prior medication. Also the number and percentage of subjects with Alopecia Areata Treatment History at Day 1 will be summarized. These will be summarized under the Safety Population.

Listing of full details of prior and concomitant medications (medication taken, therapeutic class, Drug name, start and stop dates and times with ongoing status, indication, routes, frequency, dosage and due to AE) and concomitant procedure (procedure names, indication, and date of procedure) will be provided sorted by Subject ID for Safety Population, along with age, sex, race and baseline weight of the Subject, separately. Similarly, listing of full details of Alopecia Areata Treatment History at Day 1 will also be provided.

15 TREATMENT COMPLIANCE AND EXPOSURE

All data collected in study drug administration eCRF will be included in the data listing. Listing of full details of treatment compliance and exposure (whether the subjects administered IP, Arm administered, Date and Time of administration, calculated dose, injection volume (mL), whether study drug administered per protocol and reason if no) will be provided sorted by Subject ID for Safety Population, along with age, sex, race, and baseline weight of the Subject.

Summary of Study Drug Administration will be provided for Safety Population. In the summary table, the summary statistics of total number of infusions, treatment duration (weeks), treatment duration (weeks) categories will be presented. Reasons for not dosing per protocol will be presented by visit (counts and percentages).

Treatment Duration (weeks) is calculated as (the last date of IP administration minus the first date of IP administration plus 7) divided by 7.

Treatment compliance (%) is defined as the number of infusions subject received*100/ 24. Treatment compliance (%) will be presented descriptively. The number and percentage of subjects in each compliance category (0 – < 50 (%), 50 - <80 (%), 80 - <=100 (%)) will also be presented.

16 EFFICACY

Efficacy endpoints listed in 4.2.2.1 will be listed and summarised using the Safety Population. Summary statistics of change from baseline and percentage change from baseline for SALT Score will be presented.

Percentage and 95% confidence interval will be presented for the following efficacy endpoints.

- percentages of subjects with a SALT ≤ 20 and those with a SALT ≤ 10 at Weeks 4, 8, 12, 16, 20, and 24.
- percentages of subjects achieving 30% (SALT₃₀), 50% (SALT₅₀), 75% (SALT₇₅) and 90% (SALT₉₀) improvement of SALT from Baseline at Weeks 4, 8, 12, 16, 20, and 24.
- times to SALT score improvement of 30% (SALT₃₀), 50% (SALT₅₀) 75% (SALT₇₅) and 90% (SALT₉₀) improvement of SALT from Baseline.
- percentage of subjects achieving ClinRO Measure for eyebrow (EB) Hair Loss 0 or 1* with ≥ 2 -point improvement from Baseline among subjects with ClinRO Measure for EB Hair Loss ≥ 2 at Baseline at Weeks 4, 8, 12, 16, 20, and 24.
- percentage of subjects achieving ClinRO Measure for eyelash (EL) Hair Loss 0 or 1* with ≥ 2 -point improvement from Baseline among subjects with ClinRO Measure for EL Hair Loss ≥ 2 at Baseline at Weeks 4, 8, 12, 16, 20, and 24.
- percentage of subjects achieving ClinRO Measure for Body Hair Loss 0 or 1* with ≥ 2 -point improvement from Baseline at week 24 among subjects with ClinRO Measure for Body Hair Loss ≥ 2 at Baseline.
- percentage of subjects with Scalp Hair Assessment PRO of 0 or 1* with a ≥ 2 -point improvement from Baseline among subjects with a score of ≥ 3 at Baseline at Weeks 4, 8, 12, 16, 20, and 24.
- percentage of subjects achieving PRO measure for EB 0 or 1* with ≥ 2 -point improvement from Baseline among subjects with PRO measure for EB ≥ 2 at Baseline at Weeks 4, 8, 12, 16, 20, and 24.
- percentage of subjects achieving PRO measure for EL 0 or 1* with ≥ 2 -point improvement from Baseline among subjects with PRO measure EL ≥ 2 at Baseline at Weeks 4, 8, 12, 16, 20, and 24.
- percentage of subjects achieving PRO measure for Body Hair 0 or 1* with ≥ 2 -point improvement from Baseline at week 24 among subjects with PRO measure Body Hair ≥ 2 at Baseline.

* “0 point improvement from baseline”, “1 point improvement from baseline”, “ ≥ 2 points of improvement from baseline”, and “ ≥ 2 points of improvement from baseline with 0 or 1 point” will all be reported in summaries.

Time to SALT score improvement of 30% (SALT₃₀), 50% (SALT₅₀), 75% (SALT₇₅), and 90% (SALT₉₀) improvement will be summarised using the Kaplan-Meier method. For the subjects who did not achieve 30%, 50%, 75% or 90% SALT Score improvement, the week of the last SALT score assessment for the subject will be treated as censoring in these analyses. If there is no post-baseline assessment, the subject will be censored at date of first dose.

Subgroup analyses: SALT score, change from baseline and % change from baseline will be summarize by these subgroups:

- 1) By Demographics (age categories (<40, >=40), sex and race)
- 2) By Site
- 3) By Baseline SALT Score Categories (<50, >=50 - < 95, >=95)
- 4) Duration of Current AA episode (<6 months, 6 months – 1 year, > 1 year - 4 years, >4 years - 7 years)

SALT Score <=20 and <=10 and 30%, 50%, 75% and 90% improvement of SALT by visit will also be summarized by baseline SALT Score Categories (<50, >=50 - < 95, >=95).

A few SALT assessments were not assessed accurately (approval status of “No”). SALT assessments were reassessed for those cases. The SALT score analysis in this SAP is based on the SALT score data with approval status of “Yes”.

For optional scalp biopsies, listing will be prepared sorted by subject identifier for the Safety population, along with age, sex, race, and baseline weight of the Subject.

For photographs for scalp, eyebrows and eyelashes and optional photographs of body hair (growth or regrowth) and fingernails, listing will be prepared sorted by subject identifier for the Safety population, along with age, sex, race, and baseline weight of the Subject.

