#### **4.3.1. Discontinuation of Study Drug**

Subjects should be encouraged to complete study treatment. If 3 or more study doses are missed or planned to be missed, or if 2 consecutive doses are missed or planned to be missed, the Investigator in conjunction with the Sponsor study team should determine whether study drug should be discontinued permanently.

If study treatment is permanently discontinued, the subject should follow up at the next scheduled visit for end of treatment (EOT) assessments. An end of study (EOS) visit should occur approximately 4 weeks after their final study drug dose.

A subject is considered to have completed the study if he/she has completed the follow-up visit at Week 28 (Day 197).

Study drug must be discontinued if any of the following events occur:

- Subject receives or plans to receive a prohibited therapy (see Section 5.3) consistently over the course of the study.
- Subject has  $\geq$  Grade 3 hypersensitivity reactions or anaphylaxis due to study drug per Common Terminology Criteria for Adverse Events (CTCAE) criteria. [REDACTED]
- Noncompliance with study procedures and expectations.

- Subject becomes pregnant.
- Subject withdraws consent.

Other reasons study drug may be discontinued include:

- AE (the specific AE should be identified on the electronic case report form [eCRF]).
- Investigator's decision.
- Sponsor's decision.

The date and the primary reason for study drug discontinuation will be recorded on the eCRF. If a subject discontinues study drug because of an AE, the Sponsor and/or designee must be notified by email or phone as soon as possible, and the specific AE leading to study drug discontinuation should also be identified on the eCRF.

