## 9. STATISTICAL METHODS

### 9.1. General Considerations

Data will be summarised using descriptive statistics (n, mean, median, standard deviation, minimum, maximum) for continuous variables and frequencies and percentages for discrete variables. Time to event variables will be summarised using the Kaplan-Meier method. All data summaries and listings will be produced using the SAS® software Version 9.4 or higher. A separate statistical analysis plan (SAP) will be prepared describing more details.

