4 PROJECT OVERVIEW

4.1 Description of Study Design

This is a multicenter, Phase 2, open-label Proof of Concept (PoC) study of EQ101 in adult subjects with at least 35% scalp hair loss due to alopecia areata (AA). Approximately 30 subjects will be enrolled in the study. During the 24-week treatment period, subjects will be dosed once weekly with EQ101 2 mg/kg Intravenous. Subjects will then be followed up for an additional 4 weeks after treatment. Randomisation and blinding have not been conducted in this study as this is a single-arm open-label PoC study.

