6.2 General Considerations

All data collected during the study (data originating from the electronic Case Report Forms (eCRFs) or electronic transfers will be presented in the data listings. Event-based listings will be sorted by subject identifier and event start date/time (i.e., Adverse Event (AE) start date/time). Assessment-based listings will be sorted by parameter name (alphabetically unless specifically stated otherwise), subject identifier, visit, assessment date and time (if applicable).

Unless otherwise stated, the following methods will be applied:

- Continuous variables: Descriptive statistics will include the number of non-missing values (n), arithmetic mean, standard deviation, median, minimum, and maximum values.

The minimum and maximum values will be displayed to the same decimal precision as the source data, the arithmetic mean and median values will be displayed to one more decimal than the source data, and the standard deviation (SD) values will be displayed to two more decimals than the source data for the specific variable.

The appropriate precision for derived variables will be determined based on the precision of the data on which the derivations are based, and statistics will be presented in accordance with the abovementioned rules.

- Categorical variables: Descriptive statistics will include frequencies and percentages per category. The denominator in all percentage calculations will be the number of subjects in the relevant analysis population, unless specifically stated otherwise. Percentages will be rounded to one decimal place and will not be displayed for zero frequencies.
- Repeat/unscheduled assessments: When values collected at scheduled study visits/time points is missing, repeat or unscheduled assessments closest to the scheduled visit date within the visit window defined in Table 1 and Table 2 will be used for the visit to calculate summary statistics in summary tables with visits as defined in section 6.6. All collected data will be included in the data listings. If an unscheduled visit was intended to replace the missing assessment for a scheduled visit this should be documented clearly before values are used as a scheduled visit assessment.

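### The time-to-SALT analyses censor early stoppers at their last SALT, so the Week 24 Kaplan-Meier estimate can exceed the share of all dosed subjects who ever responded

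*SAP*

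**What the plan says.** Protocol section 9.1 chooses the estimator: "Time to event variables will be summarised using the Kaplan-Meier method". SAP section 16 applies it to the four SALT improvement thresholds. A subject who does not reach the threshold is handled so that "the week of the last SALT score assessment for the subject will be treated as censoring in these analyses". A second rule covers subjects never assessed after baseline: "If there is no post-baseline assessment, the subject will be censored at date of first dose". Neither rule separates subjects who complete treatment from those who stop early. The visible text has no competing-event analysis and no sensitivity analysis for these endpoints.

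Protocol section 4.3.1 sets the follow-up of a subject who stops drug permanently: an end-of-treatment (EOT) visit at the next scheduled visit, then "An end of study (EOS) visit should occur approximately 4 weeks after their final study drug dose". Section 4.3.2 repeats this. Section 4.3.3 foresees early stopping by allowing replacement.

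The same thresholds are also reported as percentages with 95% confidence intervals at Weeks 4 to 24 (SAP section 16). SAP section 6.2 gives the general rule: "The denominator in all percentage calculations will be the number of subjects in the relevant analysis population, unless specifically stated otherwise". SAP section 7.2 defines the Safety Population used for efficacy: "Consists of all subjects who receive at least one dose of study drug. This analysis population is used for safety and efficacy analysis". No other denominator is visible for the SALT response percentages.

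**The concern.** A subject censored at Week 8 leaves the risk set. Kaplan-Meier passes that subject's weight to those still being assessed who have not yet responded, most of whom are still on drug. The estimate then describes response as if the stopper had gone on to respond at the rate of those who remained. That is hard to assume for someone who no longer receives the drug.

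Protocol section 4.3.1 lists adverse events, prohibited therapy, noncompliance, pregnancy, withdrawn consent, and investigator or sponsor decision among the reasons for stopping. The study is open-label and the investigator scores SALT (Protocol sections 3.2 and 6.7). Stopping related to prospects of regrowth is therefore plausible, though the documents do not show it.

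Protocol section 1.4 justifies the absence of a control group by historical placebo data, so a cumulative response figure from this trial is likely to be read against outside rates. A Week 24 figure that rises as more subjects leave early is an awkward basis for that, particularly where tolerability is the primary objective.

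**Working it through.** The plan gives no figure to reproduce: no response rate, dropout rate or power is stated for these endpoints. The check compares two quantities on the same data.

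**Inputs**
- N = 30, from SAP section 4.1 ("Approximately 30 subjects will be enrolled in the study").
- Censoring as in SAP section 16, with events counted before censorings in the same week.
- Assumed early stoppers without a response: 3, 6 or 9 of 30 (10-30%).
- Assumed first responses: 3 (Weeks 16, 20, 24); 6 (Weeks 12, 16, 20, 20, 24, 24); or 9 (one at Week 12, two at Week 16, three each at Weeks 20 and 24).

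**Formulas**
- Kaplan-Meier response at Week 24 = 1 − ∏(1 − d/n), where d is first responses and n is subjects at risk in each response week.
- Like-for-like comparator = subjects who ever reached the threshold by Week 24 / all dosed.

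**Worked case: 6 responders, 6 stoppers; comparator 6/30 = 20.0%**
- All stoppers last assessed at Week 4 or 8: 24 remain at risk before the first response. 1 − (23/24)(22/23)(20/22)(18/20) = 1 − 18/24 = 25.0%. This is the completers-only rate, 6/24.
- Stoppers last assessed at Weeks 4, 4, 8, 12, 16 and 20: the risk sets at Weeks 12, 16, 20 and 24 are 27, 25, 23 and 20. 1 − (26/27)(24/25)(21/23)(18/20) = 24.0%.
- No stoppers, or censoring only at Week 24: 1 − 24/30 = 20.0%, equal to the comparator.

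**Range** (first figure: all stopping by Week 8; second: stopping spread over Weeks 4-20)

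| Ever-responders of 30 | 3 stoppers | 6 stoppers | 9 stoppers |
|---|---|---|---|
| 3 (10.0%) | 11.1 / 11.1% | 12.5 / 12.0% | 14.3 / 13.5% |
| 6 (20.0%) | 22.2 / 22.1% | 25.0 / 24.0% | 28.6 / 27.0% |
| 9 (30.0%) | 33.3 / 33.2% | 37.5 / 36.2% | 42.9 / 40.9% |

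The excess runs from 11.1 − 10.0 = 1.1 points to 42.9 − 30.0 = 12.9 points. When all stopping precedes the first response, the ratio to the comparator is 30/(30 − stoppers): 1.11, 1.25 or 1.43.

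**Direction.** In 20,000 random data sets Kaplan-Meier was never below the comparator. It was strictly higher exactly when at least one subject was censored before the last observed first response.

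**Check of the remedy.** With 6 responders, and stoppers held at risk without event to Week 24, the estimate is 1 − 24/30 = 20.0% for 3, 6 or 9 stoppers.

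**The case against.** Kaplan-Meier is the method the protocol names, and these are descriptive secondary endpoints in a single-arm study not formally powered for efficacy. In the 6-responder example the exact 95% interval for 6/30 is 7.7-38.6%, which contains every Kaplan-Meier value illustrated for that case. By-visit percentages and reasons for discontinuation are already planned. All of this stands. It limits the weight of the point but does not remove a bias that runs in one direction only.

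A reader might infer several stronger claims that the documents do not support:

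- **That the Kaplan-Meier figure must be too high.** It is higher only if a non-responder is censored before someone else's later first response, and no dropout rate is given. Stopping entirely before the first response is the timing that inflates most.
- **That it contradicts the SAP's Week 24 response percentage.** That percentage is response at the visit, whereas Kaplan-Meier estimates ever having responded. They can differ without dropout: 6 ever-responders with 1 response lost by Week 24 give 20.0% against 5/30 = 16.7%.
- **That the SAP scores stoppers as non-responders in its percentages.** The all-dosed denominator suggests this, but no visible text says that a missing SALT counts as non-response. Parts of SAP section 6 are not visible, so a further missing-data rule cannot be excluded.
- **That off-drug responses at Week 28 inflate the result.** The schedule of events is not visible, so a SALT at that visit cannot be confirmed. A later event also cannot change the Week 24 estimate.
- **That discontinuation should be a competing event dated at drug stop.** The EOT visit comes after stopping, so this would discard a first response seen there.

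**Conclusion.** The point holds as a conditional one. The censoring rule is explicit and makes no exception for permanent discontinuers. The Week 24 Kaplan-Meier estimate can equal or exceed the ever-responder share of all dosed subjects, but cannot fall below it. The excess of about 1 to 13 points rests on the assumed 10-30% dropout, 10-30% response and the timings shown. It is zero if no non-responder is censored before the last first response. Informative stopping is plausible rather than demonstrated. This is a worthwhile, inexpensive improvement to a descriptive secondary endpoint. Percent change in SALT at Week 24, the primary efficacy endpoint, is untouched.

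**What to change.** In SAP section 16, for time to SALT30, SALT50, SALT75 and SALT90:

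1. Add an analysis for subjects who permanently discontinue treatment and do not reach the threshold at any approved SALT up to Week 24, including their EOT visit. Keep them at risk without event and censor them at Week 24. Apply this also to discontinuers with no post-baseline SALT.
2. Base any quoted Week 24 cumulative response on that analysis.
3. Show the Kaplan-Meier curve as now written beside it, with numbers at risk and numbers censored.
4. State that the Week 24 estimate counts first responses up to the Week 24 visit only.

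Subjects who miss late SALTs without discontinuing stay censored under the existing rule. The added estimate therefore equals the all-dosed ever-responder share exactly only if no such subject is censored before the last first response.

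The cost is SAP wording, one extra display and a slightly lower curve. The method is still Kaplan-Meier, and treatment completion status and discontinuation dates are already among the disposition data in SAP section 8.

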- Assessment windows: All assessments will be included in the data listings including additional safety labs collected and the protocol specified visit windows will not be applied to exclude assessments that were not performed on the protocol specified visit days. Visit information in the CRF will be used in the tables, listings, and figures.
- Result display convention: Results will be centre aligned in all summary tables and listings. subject numbers, visit, and parameter labels and comments may be left aligned

- Conversion of categorical values: In some instances, results may be with less than or greater than signs (i.e., < 9). The original source data captured will be displayed in the data listings (i.e., <9), while values may be converted to numbers which are half of the threshold value for summary table purposes. As an example, a value of < 9 may be converted to 4.5 before calculating summary statistics. In listings, the original value (i.e., <9) is displayed instead of imputed values.
- Date and time display conventions: The following display conventions will be applied in all outputs where dates and/or times are displayed:
 - Date only: YYYY-MM-DD
 - Date and time: YYYY-MM-DD/HH:MM

If only partial information is available, unknown components of the date or time will be presented as UN (Unknown), for example “2022-UN-UN” or “UN:UN” for time.

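### Do the SAP's visit-placement rules conflict over where a reassessed SALT score belongs?

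*SAP*

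**What the plan says.** Four parts of the SAP bear on this.

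- **Section 16 (Efficacy).** A few SALT scores had an approval status of No. Of these it says "SALT assessments were reassessed for those cases", and then "The SALT score analysis in this SAP is based on the SALT score data with approval status of" Yes. The method and date of reassessment, and the visit it is assigned to, are not given.
- **Section 6.2 (General Considerations).** On assessment windows: "Visit information in the CRF will be used in the tables, listings, and figures". The same bullet says that the protocol's visit windows are not used to drop assessments made off the planned day. On repeat or unscheduled assessments, where no scheduled value exists: "repeat or unscheduled assessments closest to the scheduled visit date within the visit window defined in Table 1 and Table 2 will be used". That sentence goes on to say that this serves the summary tables whose visits are set out in section 6.6. A replacement visit must be documented as such before its value is used.
- **Section 6.6 (Visit Display Conventions).** For summary tables: "Visit window defined in section 6.7 will be applied". For listings: "For listings, CRF labels will be used".
- **Section 6.3 (Key Definitions).** Baseline is the "last available valid, non-missing observation for each subject prior to first study treatment administration" on Day 1. A Day 1 value with no recorded time counts as Baseline.

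In the Protocol, section 6.6.2 schedules scalp photographs on Day 1 and every 4 weeks, and section 6.7.1 allows an independent reviewer to check SALT scores against them. SAP section 6.7 and Tables 1 and 2 are not visible in the public copy.

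**The concern.** Taken one sentence at a time, sections 6.2 and 6.6 appear to give two different rules for the same tables: CRF visit in one, dated window in the other. They would part company whenever a score's CRF visit and its date disagree, and a score reassessed after its visit is such a case. Baseline adds a third rule based on date and time.

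The primary efficacy endpoint is percent change in SALT at Week 24, so Baseline is its denominator. Baseline also feeds the SALT30, 50, 75 and 90 response rates, the Kaplan-Meier times and the severity subgroups. The trial is single-arm and Protocol section 1.4 relies on historic placebo data, so no concurrent control would absorb an error.

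The feared outcomes are two. Two programmers might derive different Baseline or Week 24 scores for one subject. Or a scalp seen after dosing might be labelled Day 1 and used as Baseline.

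**Working it through.** The plan states no figure to reproduce, so the check is mainly a reading of the rules against each possible kind of reassessment. The arithmetic is for scale only.

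**1. Do sections 6.2 and 6.6 conflict?** The repeat/unscheduled rule in 6.2 names section 6.6 and gives the windows their job there, which is to supply a value for a missing scheduled visit. The assessment-window rule in 6.2 adds that protocol windows do not exclude off-day assessments. Together they give the CRF visit for scheduled scores and windows for filling gaps. Section 6.6 does not repeat that limit, so its sentence is loose, but the two sections can be followed together.

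**2. Apply the rules case by case.**

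| Reassessment | What the written rules give |
|---|---|
| Re-scored from the visit's photographs, filed under that visit and date | CRF visit, window and Baseline date all agree; nothing changes |
| In person on a later day, after Baseline | The rejected score is outside the analysis, so the visit lacks an approved value; the repeat rule in 6.2 takes the closest repeat within the window |
| In person after first dose, for a rejected Day 1 score | Section 6.3 bars it as Baseline; the last valid pre-dose score is used, normally Screening, up to 35 days earlier (Protocol 3.3) |

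The second row needs one sensible step: treating a rejected score as missing. The SAP does not say so in words, but restricting the analysis to approved scores has that effect.

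**3. Size of a Baseline fallback.** Assumed scores, chosen to straddle the SALT50 threshold: Week 24 SALT of 33, Day 1 SALT of 70. Improvement = (Baseline − Week 24) / Baseline.

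- Baseline 70: (70 − 33)/70 = 52.9%, SALT50 met.
- Baseline 65: (65 − 33)/65 = 49.2%, not met.
- Baseline 60: (60 − 33)/60 = 45.0%, not met.
- Crossing point: 33/0.5 = 66.
- Effect of 70 versus 60 on the mean of 30 subjects: (52.86 − 45.00)/30 = 7.86/30 = 0.26 points.

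**4. Size of a lost Week 24 responder.** One subject in 30 is 1/30 = 3.3 points. For example, 6/30 = 20.0% (exact 95% CI 7.7 to 38.6) would become 5/30 = 16.7% (5.6 to 34.7). The interval method is assumed, since the SAP names none. This loss would require a window to remove a score that the CRF assigns to Week 24, and no visible rule does that.

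**5. How many scores?** SAP section 16 says only that they were few. The schedule gives at least 30 × (Screening + Baseline + 6 visits) = 30 × 8 = 240 SALT scores.

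**The case for a change.** The strongest argument for acting is that the visible text never says how a reassessed score was obtained or dated, and the paragraph in section 16 shows no redaction. The repeat rule is triggered by a missing scheduled value, whereas a rejected score was in fact collected. The word valid in the Baseline definition may exclude the rejected score, but it does not date the replacement. The reassessments had already happened when the SAP was written, so the sponsor could state the facts in a sentence at almost no cost. If a subject did lose a Week 24 value, that subject would leave the percent-change mean but stay in the responder denominator, because "The denominator in all percentage calculations will be the number of subjects in the relevant analysis population".

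The silence on method and date is real, and so is the loose sentence in section 6.6. Three further limits should be granted: the rule against excluding off-day assessments speaks of protocol windows, the section 6.7 windows could differ from those, and they cannot be read here.

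The claimed consequences do not stand. Using a post-dose scalp as Baseline means setting aside the specific definition in section 6.3 in favour of a general sentence about visit labels. The denominator argument assumes both that a window removes the score and that no rule on missing SALT data exists in the parts of section 6 that are not visible. A written clarification would largely repeat sections 6.2 and 6.3.

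**Conclusion.** No change to the plan is needed. The apparent contradiction comes mostly from reading section 6.6 apart from the rule in section 6.2 that refers to it. What is left is a gap in detail about a few reassessed scores. Analysts can fill it from the existing rules: keep the visit for a re-score from that visit's photographs, treat a later examination as a repeat, and never take Baseline from after the first dose.

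No stated rule is shown to give a wrong result, and no reassessed Baseline or Week 24 score is documented. The one worked Baseline example shifts the primary efficacy mean by 0.26 points; it could change that subject's SALT50 status only because the assumed scores sit either side of 66. Efficacy is a secondary objective, not formally powered, and summarised descriptively with confidence intervals. All collected scores appear in the listings, so any individual case can be traced.

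This conclusion assumes that rejected scores are treated as missing and that section 6.7 does not turn its windows into an exclusion rule for scheduled scores. It would need another look if a Day 1 score had been re-examined after dosing and entered as Baseline, contrary to section 6.3.
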